In the pediatric population, we are considerate of the invasive nature of enema therapy and the potential associated risks of anxiety and discomfort. An oral delivery would be an attractive, low risk and non-invasive alternative method of delivery for FMT therapy in this patient population. Based on our recent work in treating recurrent CDI successfully with oral inoculum by nasogastric tube delivery (16) and also by encapsulated oral inocula (work completed under FDA IND 15-199), the oral route of FMT seems to be non-inferior and obviates the need for persistent invasive delivery method. Vandenplas' case report showing ultimate remission of infantile IBD after 7 FMT (6 by an upper gastrointestinal delivery

route) provides "proof-of-concept" that this method of FMT delivery in a pediatric population is feasible, and potentially helpful in the treatment of IBD.

No studies to our knowledge have been done on FMT for pediatric IBD using frozen inocula collected from a universal donor. One might argue that given the known similarities of one's microbiome to their parents, a universal donor is more likely to introduce a more desirable commensal inoculum. (17,18) Moreover, given the frequency of IBD and other autoimmune conditions in first-degree relatives, it is common that a suitable healthy donor cannot be identified and an unrelated donor is required.

To best reflect and duplicate previous successes documented in the literature, we envision a hybrid FMT delivery method, using both FMT enema induction and an innovative oral encapsulated inoculum thereafter. We believe initial engraftment with donor stool is of paramount importance for eventual success of FMT therapy.

Fecal Microbiota Transplant (FMT) as a therapy for Ulcerative Colitis

Ulcerative Colitis (UC), a chronic inflammatory bowel disease (IBD) of the colon has similar strong microbial drivers of inflammation to CDI. FMT has been studied as a therapy for IBD in a number of small case series over the last three decades. (7,9,19) We propose that FMT would be a safe and well-tolerated therapy for pediatric UC. We further hypothesize that subjects will demonstrate subjective measures of clinical improvement (i.e., in the Pediatric Ulcerative Colitis Activity Index), in patient related outcome variables such as abdominal pain and number of daily bowel movements, as well as in objective inflammatory biomarkers.

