7. STATISTICAL CONSIDERATIONS

7.1. Power Calculation

The primary aim of this phase I/II study is to establish whether or not FMT is a safe treatment for children and young adults with UC. Based on clinical experience, adverse events (AEs) in IBD patients are common and include abdominal pain, cramping, diarrhea, fever, bloody stool, vomiting, frequent defecation, joint pain, and eye pain. It's estimated that 70% of patients in any given year will experience a flare of their disease and have some or a combination of these symptoms. Safety, therefore, needs to be assessed relative to the high prevalence of AEs in this population. For the primary outcome, we will take any new reported SAEs or worsening of the existing AEs during the study period following enrollment into account.

The study will be powered for equivalence in the proportion of new SAEs or worsening of the existing AEs, assuming null (Ho) and alternative (Ha) hypotheses defined as follows:

$$\begin{split} & \text{Ho: } p1-p2 \leq \text{-}\delta_L \ \text{ or } p1-p2 \geq \delta_U. \\ & \text{Ha: } \delta_L \leq p1-p2 \leq \delta_U \end{split}$$

where p1 is the proportion of new SAEs or worsening of the existing AEs in the placebo group, p2 is the proportion in the FMT group, δ_L is the lower margin and δ_U is the upper margin. We expect to enroll a total of 60 patients into this study for a total of 30 FMT and 30 placebo patients. Assuming the rate of new incident SAEs or worsening of existing AEs in the placebo group is 10%, there will be 82% power to reject Ho that the difference in proportions is 0.20 or greater from zero in the same direction. Similarly, we will have an 85% power to reject a difference of 0.25 or greater if the rate of new incident SAEs or worsening of existing AEs increases to 15%.

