7.3. Data Analysis

All patients who are eligible, randomized, and have received at least one-dose of the study medication including antibiotics/placebo in the first week will be included into the analysis for primary outcomes to assess the safety and tolerability of FMT, as this will be a per protocol (and not intent-to-treat) analysis . Continuous variables will be presented as mean and standard deviation (SD) or median and interquartile range (IQR), depending on the distribution of the data. Categorical variables will be presented as number and percentage. Disease severity (PUCAI) and patient characteristics at baseline will be compared between the treatment groups to determine whether or not randomization resulted in balanced groups. Methods of 2-group comparison will include Student's t-test, the Mann-Whitney test, Pearson chi-square test, and Fisher exact test, depending on the distribution of the variable under consideration. The primary outcome of safety will be assessed via a 2×2 cross-tabulation, where the proportion of patients with new incident SAEs or upgrade of existing AEs in the FMT group will be compared to the proportion in the placebo group. Two one-sided tests for equivalence (32) will be constructed and the overall *P* value taken to be the larger of the lower and upper tests. Statistical significance will be assessed at *P*<0.05.

For the second outcome, we will use longitudinal data analysis methods to investigate changes in inflammatory biomarkers including stool calprotectin, stool lactoferrin, serum ESR/CRP, albumin, and hematocrit over the study period. Generalized Estimating Equations will be performed to examine the association between FMT and changes in these biomarkers.

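### A one-directional safety question is tested as two-sided equivalence, so the primary test can fail because FMT has fewer events; at the planned rates the main cost is power (about 65% and 71%, not 82% and 85%)

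*Combined protocol and SAP*

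**What the plan says.** Section 2.1 makes safety and tolerability against placebo the primary aim, and section 7.1 restates it as whether FMT is safe. The test is then framed as equivalence: "The study will be powered for equivalence in the proportion of new SAEs or worsening of the existing AEs". The null hypothesis has two parts, a placebo-minus-FMT difference at or below the lower margin and one at or above the upper margin. Here p1 is the placebo proportion and "p2 is the proportion in the FMT group, δ_L is the lower margin and δ_U is the upper margin". Markedly fewer events on FMT is therefore part of the null. Section 7.3 continues: "Two one-sided tests for equivalence (32) will be constructed and the overall" P value is the larger of the two, judged at 0.05.

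On the event, section 7.1 says "For the primary outcome, we will take any new reported SAEs or worsening of the existing AEs during the study period following enrollment into account". Relatedness to FMT is not required. The same section says that "adverse events (AEs) in IBD patients are common and include abdominal pain, cramping, diarrhea, fever, bloody stool, vomiting, frequent defecation, joint pain, and eye pain", and estimates that "70% of patients in any given year will experience a flare of their disease and have some or a combination of these symptoms".

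Section 1.1 expects FMT to act on some of those symptoms. "We further hypothesize that subjects will demonstrate subjective measures of clinical improvement", it says, and also "in patient related outcome variables such as abdominal pain and number of daily bowel movements, as well as in objective inflammatory biomarkers".

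The sample size is 30 per arm. Stated power is 82% for a 10% placebo rate with margin 0.20, and 85% for a 15% rate with margin 0.25. Section 5.3.3 lists a different primary outcome, FMT-related AEs of grade 2 or above, with no hypothesis, margin or test.

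**The concern.** Safety asks whether FMT is worse than placebo. Equivalence also asks whether FMT is not much better, and fails if either part fails. Because the event includes symptoms that FMT may relieve, efficacy can push the result towards the second boundary. The documents do not say how a failure on that side would be read.

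Three things are at stake:

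- The primary test can miss significance although the data exclude harm at the margin.
- The second test costs power even when FMT has no effect, and the stated power does not allow for it.
- A single pooled proportion can let a fall in flare-type events offset a rise in events that FMT causes.

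**Working it through.** **Inputs.** From 7.1: n = 30 per arm; placebo 10% with margin 0.20, and 15% with margin 0.25. From 7.3: 5% for each one-sided test. Other rates below are assumptions.

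**Formulas** (unpooled normal approximation, m = margin):
- SE = √[p1(1−p1)/30 + p2(1−p2)/30]
- Harm side = Φ((m + p1 − p2)/SE − 1.645)
- Benefit side = Φ((m − p1 + p2)/SE − 1.645)
- Equivalence (TOST) power = max(0, harm side + benefit side − 1)

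**Step 1: reproduce the stated power.**
- 10% in both arms, m = 0.20: SE = 0.0775. One test: Φ(0.20/0.0775 − 1.645) = 82.6%. TOST: 2 × 0.826 − 1 = 65.1%.
- 15% in both arms, m = 0.25: SE = 0.0922. One test: 85.7%. TOST: 71.4%.

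A noncentral t version of the single test gives 81.8% and 85.0%. The stated 82% and 85% are thus one-sided powers. Under TOST, 82% needs 41 per arm and 85% needs 39. Exact binomial enumeration with Wald tests gives 67% and 70% for TOST, and 84% and 85% for the single test. With Farrington–Manning score tests the figures are 56% and 69%, and 78% and 85%.

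**Step 2: can fewer events on FMT fail the test?** Take 4/30 on placebo and 0/30 on FMT. The difference is 0.133, SE = √(0.1333 × 0.8667/30) = 0.0621, and the 90% CI is 0.133 ± 1.645 × 0.0621 = 0.031 to 0.235. The upper limit exceeds 0.20, so TOST fails although the harm side passes; the score test agrees. At margin 0.25 this result would pass, but 5/30 v 0/30 (90% CI 0.055 to 0.279) fails at both margins.

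**Step 3: how much does a true benefit cost?** Each case is set against no benefit at the same placebo rate.

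| Margin | Placebo | FMT | Harm side | TOST |
|---|---|---|---|---|
| 0.20 | 10% | 10% | 82.6% | 65.1% |
| 0.20 | 10% | 5% | 98.0% | 69.6% |
| 0.20 | 10% | 2% | 99.9% | 63.2% |
| 0.25 | 15% | 15% | 85.7% | 71.4% |
| 0.25 | 15% | 10% | 97.0% | 72.9% |
| 0.25 | 15% | 5% | 99.8% | 62.4% |
| 0.25 | 20% | 20% | 78.1% | 56.2% |
| 0.25 | 20% | 5% | 99.9% | 32.8% |
| 0.25 | 30% | 30% | 68.0% | 36.0% |
| 0.25 | 30% | 10% | 99.8% | 12.4% |

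At the planned rates benefit shifts TOST power by a few points either way, and by 9 points at 15% v 5%. The larger losses need placebo rates of 20–30%. For orientation, a constant hazard of 70% per year implies 1 − 0.3^(8/52) = 17% flaring in 8 weeks and 1 − 0.3^0.5 = 45% in 26 weeks. Not every flare need count as an event.

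**Step 4: offsetting** (assumed rates, flare and FMT-caused events independent, m = 0.20, exact Wald). FMT-arm composite = 1 − (1 − flare)(1 − harm), with placebo flare at 10%.
- FMT flare 0%, harm 10%: 10% in both arms. TOST passes 67% of the time, the same as with no harm.
- Harm 25%, flare unchanged: composite 32.5%, difference 22.5 points, inside the null. TOST passes 3%.
- Harm 25%, flare cut to 2%: composite 26.5%, difference 16.5 points, outside the null. TOST passes about 10%; the harm-side test alone passes 12%.

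The offset cannot exceed the available flare reduction, here 10 points. A one-sided test does not remove it.

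**The case against.** The strongest reply is that little goes wrong at the planned rates. A true reduction cannot exceed 10 or 15 points there, so no benefit lies in the null at margins 0.20 or 0.25, and moderate benefit slightly raises TOST power. This stands. A reader might infer that the plan becomes steadily less able to support safety as FMT works better, or that fewer events count as failure in general. The documents support neither at their own rates.

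A reader might also cite 30% v 10% at margin 0.20, where TOST power is about 4%. With no benefit it is also about 4%, so that case shows low power and not a penalty for benefit. Nor does failing TOST mean that FMT is declared unsafe: equivalence is simply not shown, and the harm-side P value is computed anyway.

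On offsetting, section 5.3.3 lists FMT-related events, section 6.1 has a blinded investigator judge relatedness, and the DSMB reviews events (6.2). These are real but partial safeguards, since none carries a formal test and the symptoms judged overlap with flare. Harm of 8 or 10 points would in any case lie inside the plan's own margin.

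Finally, disease worsening can itself be a harm: section 4.1.5 cites a UC flare after FMT. Counting it is defensible. The documents give no event mix, so they do not establish that the primary event is mostly disease worsening.

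What survives is the mismatch between question and test, the misstated power, and the missing split of events.

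**Conclusion.** The concern holds in limited form. The primary safety test includes a boundary that no objective asks for, and a result in FMT's favour can fail it. At the planned rates the size of the problem is power: about 65% and 71% for the declared procedure against the stated 82% and 85%. Benefit adds at most about 9 points of further loss in the planned-rate cases examined. Larger losses (56% to 33%, or 36% to 12%, at margin 0.25) rest on assumed placebo rates of 20% and 30% with strong benefit.

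Offsetting is possible but bounded. It is tempting to conclude that disease benefit would cancel real FMT harm and drive the primary answer; that goes beyond the documents, because the rates needed are assumed and harm is also looked at outside the pooled test.

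The power figures assume 30 evaluable per arm, 5% per side and the normal approximation. The plan names no test statistic, and with a score test power at the 10% rate is lower for either procedure.

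**What to change.** In 7.1 and 7.3, base the safety conclusion on the harm side alone: reject, at one-sided 5%, the null that p2 − p1 (FMT minus placebo) is at or above the margin. State which margin applies and name the test statistic. Under the normal approximation this makes the stated 82% and 85% correct with 60 patients. Report the other side descriptively with its confidence interval.

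Keep the total event as primary, and tabulate UC-activity events and all other events by arm beside it. The table is what addresses offsetting. Reconcile 5.3.3 with 7.1 and 7.3, so that it is clear which event is tested and how FMT-related grade 2 or higher events are reported.

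The cost is wording and one table. The trial gives up the claim that FMT does not have substantially fewer events than placebo, which no objective seeks. If equivalence is kept, 41 per arm (82 in total) or 39 per arm (78) are needed for the stated power. If a one-sided 2.5% level is preferred, 30 per arm gives 73.3% and 77.4%, and 38 or 37 per arm restore 82% and 85%.

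### The 82% and 85% power in Section 7.1 match a single one-sided test; the planned equivalence analysis needs both tests to succeed and has about 65% and 71% power

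*Combined protocol and SAP*

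**What the plan says.** Section 7.1 (Power Calculation) states the aim of the calculation: "The study will be powered for equivalence in the proportion of new SAEs or worsening of the existing AEs". The null hypothesis has two parts, one at a lower and one at an upper margin for the placebo proportion minus the FMT proportion.

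The sample size is given as "We expect to enroll a total of 60 patients into this study for a total of 30 FMT and 30 placebo patients". Two power statements follow:

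- With a placebo rate of 10%, "there will be 82% power to reject Ho that the difference in proportions is 0.20 or greater from zero in the same direction".
- With a rate of 15%, "we will have an 85% power to reject a difference of 0.25 or greater".

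Section 7.3 (Data Analysis) gives the test: "Two one-sided tests for equivalence (32) will be constructed and the overall *P* value taken to be the larger of the lower and upper tests". The significance threshold is 0.05. Neither section gives a power for passing both tests together, and neither states the true FMT rate assumed.

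**The concern.** Taking the larger of the two P values means that equivalence is shown only when both one-sided tests reject. The power sentence in Section 7.1 speaks of a difference in one direction, which describes one of those tests. When the true rates are equal, each test can fail on its own, so the chance of passing both is well below the chance of passing either.

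This is the only power justification for the 60 patients, and safety is the primary aim. If the figure belongs to a different test from the planned one, the DSMB and IRB are relying on an overstated chance of success. A failure to show equivalence could also be misread as a safety signal in a largely paediatric trial when it reflects low power.

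**Working it through.** **Inputs.** From Section 7.1: n = 30 per arm; rate 10% with margin 0.20; rate 15% with margin 0.25. From Section 7.3: two one-sided tests, both required, each at 0.05 (critical value 1.645). Assumption: the true FMT rate equals the placebo rate, which Section 7.1 implies but does not state.

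**Step 1: reproduce the stated figures with one one-sided test.** With unpooled variance, SE = √(2p(1−p)/30) and power = Φ(margin/SE − 1.645).

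- 10%, 0.20: SE = √(2 × 0.10 × 0.90/30) = 0.0775; Φ(0.20/0.0775 − 1.645) = 0.826. Stated: 82%.
- 15%, 0.25: SE = √(2 × 0.15 × 0.85/30) = 0.0922; Φ(0.25/0.0922 − 1.645) = 0.857. Stated: 85%.

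The noncentral t with 58 degrees of freedom gives 81.8% and 85.0%, which fits both stated figures.

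**Step 2: power of the planned analysis.** With a true difference of zero, the two ways of failing are equally likely and do not overlap, so the power to pass both is 2 × (one-sided power) − 1.

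- 10%, 0.20: 2 × 0.8257 − 1 = 0.651.
- 15%, 0.25: 2 × 0.8570 − 1 = 0.714.

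**Step 3: check against exact binomial results.** All 31 × 31 outcomes were enumerated at equal rates.

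| Scenario | Stated | One test, normal | Both tests, normal | Both tests, exact (Wald) | Both tests, exact (Farrington-Manning score) |
|---|---|---|---|---|---|
| 10%, margin 0.20 | 82% | 82.6% | 65.1% | 67.4% | 56.3% |
| 15%, margin 0.25 | 85% | 85.7% | 71.4% | 69.5% | 69.2% |

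**Step 4: vary the FMT rate.** With the placebo rate held at 10% and the FMT rate varied from 0 to 30%, two-test power (normal approximation) peaks at about 70%, at an FMT rate of 6% to 7%. With the placebo rate at 15% it peaks at about 74%, at an FMT rate near 12%. No FMT rate gives 82% or 85%.

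**Step 5: what the stated power would take.** By the normal approximation, two-test power of 82% at 10%/0.20 needs 41 per arm (83.0%; 40 per arm gives 81.9%). Power of 85% at 15%/0.25 needs 39 per arm (85.2%). With 30 per arm at a 10% rate, 82% requires one-sided power of (1 + 0.82)/2 = 0.91. The margin is then (1.645 + 1.341) × 0.0775 ≈ 0.23.

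**The case against.** **The origin of the figures is inferred.** Two one-sided tests at 0.10 per side would give 80.7% and 84.7%, also near the stated pair. The single-test reading fits the first figure better and agrees with the one-direction wording, but it is not proven. This does not help the plan: Section 7.3 fixes 0.05, and at 0.05 the planned analysis has about 65% and 71% power however the stated figures arose.

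**The consequence can be overstated.** Under equal rates, half of the failures fall on the side where FMT looks safer than placebo. At 10%/0.20, the chance of failing to exclude excess harm from FMT is about 17% by the normal approximation (16% Wald, 22% score), close to what Section 7.1 implies. That stands. The 1 in 3 figure applies to the equivalence claim, which is the claim the plan makes.

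**65% is too exact for the first scenario.** This also stands. Section 7.3 does not name the test statistic, and exact values run from 56% to 67%. A restatement should name the statistic or give the range.

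**The study is a small phase I/II trial.** That is a reason not to ask for more patients. It does not justify a power figure for a different test.

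**Conclusion.** The stated power does not belong to the planned analysis. At 0.05 per side, 30 per arm and equal true rates, power for equivalence is about 65% rather than 82% (10%, margin 0.20) and about 71% rather than 85% (15%, margin 0.25). The shortfalls are about 17 and 14 points.

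The chance of missing equivalence when the arms are equally safe is 35% and 29%, against the 18% and 15% implied. These are normal-approximation values, and the exact results in the table are no closer to the stated figures. Section 7.1 shows no allowance for dropout, and any loss would lower power further.

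At the planning rate the second test also guards against a state that cannot occur: with a 10% placebo rate, placebo minus FMT cannot exceed 0.10, so it cannot reach 0.20. That argument holds only where the placebo rate is below the margin.

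**What to change.** In Section 7.1, replace 82% and 85% with the power of the two-test procedure: about 65% at 10%/0.20 and about 71% at 15%/0.25, with 30 per arm. State that the true rates are assumed equal and that each test is at 0.05. Name the test statistic in Section 7.3 and give its exact power; at 10%/0.20 this is 67% for Wald or 56% for the score test. The cost is a less favourable stated power. The 60 patients and the conduct of the trial do not change.

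The alternative is to make the primary test in Section 7.3 a single one-sided non-inferiority test on the harm side (null: FMT rate minus placebo rate at least 0.20, one-sided 0.05). That is the test the 82% appears to describe, and it also needs no more patients. It is a change of hypothesis, however, and gives up the equivalence claim. It also does not secure 82% with every statistic. By exact enumeration at 10%/0.20, the Wald test has 83.7% power but rejects 6.2% of the time at the null boundary (10% against 30%). The score test holds its level (4.8%) but has 78.2% power. If this route is chosen, the statistic and its exact power should be stated.

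### The primary equivalence test has two candidate margins, 0.20 and 0.25; the plan does not say which governs, and the printed power fits neither under the planned test

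*Combined protocol and SAP*

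**What the plan says.** Section 7.1 sets an equivalence objective: "The study will be powered for equivalence in the proportion of new SAEs or worsening of the existing AEs". Ho and Ha are written for p1 − p2 (placebo minus FMT), and the limits are described only in words: "δ_L is the lower margin and δ_U is the upper margin". No sentence equates either symbol with a number.

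Two numbers then appear in consecutive power statements for the same 30 + 30 patients:

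- At a 10% placebo rate: "there will be 82% power to reject Ho that the difference in proportions is 0.20 or greater from zero in the same direction".
- At a 15% rate, presented as a parallel case: "we will have an 85% power to reject a difference of 0.25 or greater if the rate of new incident SAEs" (the sentence then adds AE worsening and the 15% figure).

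Only the first names Ho. Section 7.3 defines the primary comparison: "Two one-sided tests for equivalence (32) will be constructed and the overall" P value is the larger of the two, judged at 0.05. It gives no margin and does not refer back to 7.1. No other section supplies one.

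**The concern.** A TOST P value cannot be calculated until a margin is chosen, so the margin is the decision threshold of the primary safety analysis. Here the plan offers two values and no rule for choosing between them. Two analysts following the text could test the same table at 0.20 and at 0.25 and disagree on whether FMT is equivalent to placebo for safety. A final report can say which margin it used, but a reader could not confirm from the plan that this one was fixed in advance.

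The power statements do not help to identify the margin. They rest on different margins, so 82% and 85% cannot be compared with each other, and both look high for a two-sided equivalence test with 30 per arm.

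**Working it through.** **Inputs.** n = 30 per arm, event rates 10% and 15%, differences 0.20 and 0.25, stated power 82% and 85% (section 7.1). TOST, larger P compared with 0.05, so each side is tested at 0.05 (section 7.3). Assumption: the true difference is zero. The plan does not state this, but it is the value that reproduces its figures.

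**Step 1. Reproduce the printed power.** Normal approximation, unpooled variance:

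SE = √(2p(1 − p)/30); one-sided power = Φ(margin/SE − 1.645).

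- p = 0.10, margin 0.20: SE = √0.006 = 0.0775; Φ(2.582 − 1.645) = 0.826. Printed: 82%.
- p = 0.15, margin 0.25: SE = √0.0085 = 0.0922; Φ(2.712 − 1.645) = 0.857. Printed: 85%.

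Both printed figures are recovered, each with its own margin and for a single one-sided test. So the calculation itself used two margins.

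**Step 2. Power of the planned test.** At zero true difference, TOST power ≈ 2 × (one-sided power) − 1.

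| Event rate | Margin | One-sided | TOST |
|---|---|---|---|
| 10% | 0.20 | 82.6% | 65.1% |
| 10% | 0.25 | 94.3% | 88.6% |
| 15% | 0.20 | 70.0% | 40.0% |
| 15% | 0.25 | 85.7% | 71.4% |

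For the two scenarios as printed, the TOST has 65.1% and 71.4%. Exact enumeration of all 31 × 31 outcomes gives 56.3% (score) or 67.4% (Wald) for the first and 69.2% or 69.5% for the second.

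**Step 3. Does the margin change the verdict?** Section 7.3 names no test statistic, so both score and Wald are shown. Wald example, 3/30 placebo v 5/30 FMT: difference = −0.0667; SE = √(0.1 × 0.9/30 + 0.1667 × 0.8333/30) = 0.0873. At 0.20, z = 0.1333/0.0873 = 1.53, P = 0.063. At 0.25, z = 0.1833/0.0873 = 2.10, P = 0.018. Equivalently, the 90% interval is −0.210 to 0.077, which crosses −0.20 but not −0.25.

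| Placebo v FMT (of 30) | Overall P at 0.20, score / Wald | Overall P at 0.25, score / Wald | Verdict |
|---|---|---|---|
| 3 v 5 | 0.076 / 0.063 | 0.027 / 0.018 | changes |
| 4 v 6 | 0.089 / 0.082 | 0.034 / 0.028 | changes |
| 3 v 4 | 0.034 / 0.022 | 0.011 / 0.004 | equivalent at both |
| 5 v 5 | 0.024 / 0.019 | 0.007 / 0.005 | equivalent at both |

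3 v 3 and 4 v 4 are also equivalent at both margins. With 3/30 on placebo, the largest FMT count still called equivalent is 4 at 0.20 and 5 at 0.25; with 4/30 it is 5 and 6. The margin therefore moves the limit by one FMT event, at counts near the rates the plan assumes (3/30 is its 10%).

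**The case against.** The strongest reply is that the margin is given, if indirectly. Ho is defined by the margins, and the 82% sentence describes rejecting Ho as rejecting a difference of 0.20 or more. Substitution gives δ_L = δ_U = 0.20. The 0.25 sentence does not name Ho and is conditional on a higher event rate, so it may be only a what-if.

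Much of this stands. A reader might infer that the primary test cannot be run at all from the text; the documents do not support that, because an analyst could reasonably take 0.20. A reader might also take up the share of trials whose verdict depends on the margin. With truly equal arms this is 28% (score) or 18% (Wald) at a 10% rate and 34% or 25% at 15%. Those shares describe a risk only if 0.25 is a live choice for the analysis. If 0.20 was always intended, they show what departing from the plan would do.

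The reply does not remove the ambiguity. A what-if about the event rate would hold the margin fixed and let the power fall; at 0.20 and a 15% rate, the plan's own one-sided formula gives 70.0%. Instead the margin moves to 0.25, in a sentence offered as parallel to the first. If the margin was meant to depend on the event rate, that would be a legitimate design, but it needs a stated rule (for an observed 12%, say), and there is none.

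The phrase about direction in the 82% sentence partly discloses a one-directional calculation. It does not reconcile that calculation with a two-sided Ho or with the TOST. The power mismatch would remain even with a clearly stated margin, so it is a linked but separate fault.

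**Conclusion.** The point holds as an ambiguity in the primary decision threshold that should be corrected. Section 7.1 implies 0.20 through its Ho sentence, uses 0.25 in the next, and section 7.3 names neither. Borderline tables such as 3 v 5 and 4 v 6 change verdict between the two values, while the more even tables checked do not. If 0.20 is the intended limit (an assumption), testing at 0.25 would claim equivalence in 12.8% (score) or 12.9% (Wald) of trials when the true rates are 10% and 30%, against 3.8% or 5.4% at 0.20.

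The printed power is that of one one-sided test. For the planned TOST it is about 65% and not 82% in the first scenario, and about 71% and not 85% in the second. These figures rest on 30 evaluable patients per arm, zero true difference and the plan's own event rates. Confidence that the text is ambiguous is high.

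**What to change.** - In 7.1 and again in 7.3, state one numerical margin, δ_L = δ_U = 0.20 (the value tied to Ho), unless the sponsor justifies another. Fix it before any comparison by arm. If a rate-dependent margin was intended, write out and justify the rule.
- Name the test statistic in 7.3, since score and Wald P values differ.
- Replace 82% and 85% with TOST power under the chosen margin at both rates: at 0.20, about 65% at a 10% rate and 40% at 15%; at 0.25, about 89% and 71%.
- Show the other margin only as a labelled sensitivity analysis.

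The cost is a sentence or two in each section, with no extra patients or data. The drawback is less favourable stated power at 0.20. Choosing 0.25 recovers some of it, but the sponsor must then justify a 25-point difference in event rates as acceptable.
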